	
6 consecutive Monthly visits. Each Quarterly visit will take place by the middle of the first month (<math>\pm</math> 7 days) of each calendar quarter (i.e., January 15, April 15, July 15 and October 15).
 
For patients who did not complete Study RP103-03, study visits will consist of:
 
 
• Screening Visit which may occur up to 28 days prior to Day 1.
 
• Dose Confirmation Period (Days 1-5) which includes 3 study visits over 5 days.
 
• Day 1 includes a morning study visit while the patient is fasted, with pre-dose blood samples collected for trough cysteamine and peak WBC cystine determination while the subject is still taking Cystagon®. RP103 treatment regimen begins at the clinic on the morning of Day 1, administered Q12H at a starting total daily RP103 dose equal to 70% of the Screening total daily Cystagon® dose. Patients will leave the clinic for Days 2-3 and take RP103 as instructed.
 
• Days 4 and 5 each include a morning study visit; RP103 Q12H treatment regimen continues.
 
• Quarterly Study Visits which will take place by the middle of the first month (<math>\pm</math> 7 days) of each calendar quarter (i.e., January 15, April 15, July 15 and October 15).
 
 
All patients, including those who did and those who did not complete Study RP103-03, will have an End of Study (EOS) Visit conducted within 7 (<math>\pm</math> 2 days) from the last completed study visit or from the date of decision to terminate.

Planned Sample Size:	Up to 60 patients may be enrolled. Initial sample size depends on the number of patients entering the Study from the RP103-03 Safety and Efficacy Study. Additional patients may be enrolled after all patients from Study RP103-03 have completed participation and results demonstrate non-inferiority of RP103 versus Cystagon® in reducing WBC cystine levels.
Total Number Of Centers:	Up to 10 sites in North America and Europe
Selection Criteria:	
Inclusion Criteria:
 
 
1. Male and female subjects must have completed the last visit of Study RP103-03 and be willing to continue with RP103 treatment.
 
 
OR for patients who did not complete the RP103-03 study:

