Study Endpoints:	
Safety Endpoints:
 
 
• The safety profile of RP103 will be investigated by safety reviews conducted by the Investigator at or prior to each Monthly or Quarterly visit and through adverse event report monitoring (including attribution of treatment-emergent adverse events and serious adverse events [SAEs]), physical examination (including basic neurological and skin assessment findings), vital signs, ECG and clinical laboratory testing as outlined in the Schedule of Events.
 
 
Pharmacokinetic Endpoint:
 
 
• The trough plasma cysteamine concentration will be measured from samples collected 0.5 hour post dose at each study visit.
 
 
Pharmacodynamic Endpoint:
 
 
• The WBC cystine content will be measured from samples collected 0.5 hour post dose at each study visit.
 
 
[REDACTED]:
 
 
• [REDACTED]
 

Duration of the Study:	
Patients will be followed until Study termination; which can occur by patient, physician or Sponsor request, or until the RP103 drug is available through the appropriate marketing approval, or until the Sponsor terminates development of RP103 for this indication for any reason. Approximate treatment time in the Study is up to 96 months. However, a subject may withdraw consent or be withdrawn from the study prior to completion.

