**Table 6: Number of unique subjects with at least one Serious Adverse Event (SAE) in all patients (ITT population)**

As with Cystagon®, adverse events under RP103 were mostly nausea, vomiting and GI side effects. A total of 130 adverse events (AEs) and serious adverse events (SAEs) were reported during the trial (Table 7 - NB: In this table some AEs are counted twice when the AE started during the Run-In period and ended during Crossover Period 1). Almost half of these AEs (59/130, 45%) were GI symptoms. Looking at the 54 GI AEs that happened during the crossover periods only, 70% (38/54) of these GI symptoms were considered by the Principal Investigator as possibly or probably related to the drug (44% RP103, 15% Cystagon® and 9% to both Cystagon® and RP103). Also, 14 of 24 (60%) drug-related GI AEs occurred in 2 patients only, which accounts for most of the difference between Cystagon and RP103 for this category of AEs.

MedDRA System Organ Class	2-week Run-In (Cystagon®)		3-week Crossover (Cystagon®)		3-week Crossover (RP103)		Both Crossover Periods	
	Related	Not	Related	Not	Related	Not	Related	Not
Number of ITT patients at risk	43		41		43		41	
Number of AE Episodes	17		26		75		18	
Gastrointestinal disorders	1	4	8	3	24	10	5	4
Metabolism and nutrition disorders	0	0	1	4	0	3	1	1
Nervous system disorders	0	2	0	1	2	4	0	2
Cardiac disorders	0	0	0	3	0	1	1	0
General disorders and administration site conditions	0	0	0	0	1	2	0	1
Infections and infestations	0	3	0	1	0	3	0	0
Renal and urinary disorders	0	0	0	1	1	1	1	0
Skin and subcutaneous tissue disorders	0	0	0	1	1	1	0	1
Vascular disorders	0	1	0	1	1	2	0	1
Musculoskeletal and connective tissue disorders	0	0	0	0	0	2	0	1
Respiratory, thoracic and mediastinal disorders	0	5	0	2	0	5	0	0
Injury, poisoning and procedural complications	0	1	0	0	0	3	0	0
Investigations	0	0	0	0	0	1	0	1
Ear and labyrinth disorders	0	0	0	0	0	0	0	1
Eye disorders	0	0	0	0	0	0	0	1
Psychiatric disorders	0	0	0	0	0	1	0	0

Note: Any AE starting and resolving in one of the 3 periods Run-In, Cross-Over Period 1 and Cross-Over Period 2 would be counted once for that period. Any AE starting in the Run-In and resolving in the Cross-Over period 1 would be counted once in both periods. Any AE starting either in the Run-In or in the Cross-Over treatment period 1 and resolving in the Cross-Over treatment period 2, would be counted once in the 'Both Cross-Over periods' column.

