### **11. Statistical Plan**

#### **11.1. Statistical Methods**

This Study is designed to assess the safety and tolerability of Cysteamine Bitartrate Delayed-release Capsules (RP103) in patients with cystinosis.

A statistical analysis plan will be developed that describes in detail, the statistical methods to be used and will be finalized prior to database lock. This document may modify the plans outlined in the protocol; however, any major modifications of the Study endpoint definitions will be reflected in a protocol amendment.

Demographic and disposition data, drug administration, medical history, prior and concomitant medications, AEs, clinical laboratory measurements, vital signs, ECG measurements and physical examination findings will be summarized. Descriptive summaries of mean and mean changes from screening will be presented for the safety laboratory parameters (hematology, serum chemistry and urinalysis, as applicable),

vital signs and ECGs. The overall incidence of subjects with adverse events will be summarized by System Organ Class (SOC) and Preferred Term (PT) using the latest version of the Medical Dictionary for Regulatory Activities (MedDRA) coding dictionary. Summaries by maximum severity, drug –relationship (as determined by the investigator) and drug discontinuation will also be presented. In addition, summaries of annualized exposure adjusted AE rates as well as summaries of the incidence of subjects with AEs by study year of onset (Year 1, Year 2 and Year 3 or later) will be generated. The overall incidence of subjects with serious adverse events (SAEs) will be summarized by SOC and PT. The annualized exposure adjusted SAE rates as well as the incidence by study year will also be tabulated. Safety laboratory values outside reference ranges will be flagged in laboratory listings.

AEs will be categorized using MedDRA, and listed by verbatim, primary term and SOC. SAEs will include MedDRA coding of primary and secondary (non serious) event terms.

[REDACTED]

[REDACTED]

[REDACTED]

[REDACTED]

Cysteamine concentrations and WBC cystine levels will be summarized per patient.

*Pharmacokinetics:*

The steady-state plasma concentration profiles of cysteamine will be determined for each patient and the  $AUC_{0-t}$ ,  $C_{min}$ ,  $C_{max}$ ,  $T_{max}$  and  $t_{1/2}$  PK parameters will be estimated using non-compartmental methods.

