### 9.1. Study Drug Exposure

Duration of study drug exposure will be calculated as the duration from the date of first dose of RP103 in Study RP103-04 to the date of last dose as:

Exposure (days) = (Last Dose Date – First Dose Date + 1) – number of days dosed with Cystagon

Duration of exposure will be summarized for each subpopulation and overall using descriptive statistics. The number and percentage of subjects with duration of exposure in each category ( $\leq$  12 months,  $>$  12 months and  $\leq$  24 months,  $>$  24 months and  $\leq$  36 months,  $>$  36 months and  $\leq$  48 months,  $>$  48 months and  $\leq$  60 months, and  $>$  60 months) will also be summarized.

The mean RP103 dose (mg/m^2/day) will be summarized over time using collected visits.

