The number and percentage of subjects with any treatment-emergent adverse events will be summarized by relationship to study drug (not related, unlikely related, possibly related, probably related, definitely related, unknown) and severity (mild, moderate, severe, life-threatening, death, unknown) by SOC and PT. In these tabulations, each subject will contribute only once (i.e., the most related occurrence or the most intense occurrence) to each of the incidence rates in the descriptive analysis, regardless of the number of episodes – e.g. worst grade, per subject, per toxicity.

In addition, summaries of the incidence of subjects with AEs, and SAEs, by study year of onset (Year 1, Year 2 and Year 3 or later) will be generated. Treatment-emergent gastro-intestinal adverse events, i.e. adverse events with SOC of “gastrointestinal disorders”, will also be summarized by frequency of episodes (1-3 occurrences vs 4 or more) by PT. Similarly, treatment-emergent treatment-related gastro-intestinal adverse events will be summarized.

All adverse events occurring on study will be listed in subject data listings.

By-subject listings also will be provided for the following: serious adverse events, adverse events for laboratory abnormalities, and adverse events leading to study discontinuation.

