## 10. CHANGES TO PLANNED ANALYSES

The following changes from Amendment 9 of the protocol have been made:

- [REDACTED]
- Use of gastric acid reducing medications was changed from an exploratory endpoint (per the protocol) to a safety endpoint.
- Analysis of annualized exposure adjusted AEs will not be performed.

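### The GI episode split (1-3 versus 4 or more, by Preferred Term) is not adjusted for exposure and can miss GI burden spread over several terms

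*SAP*

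**What the plan says.** SAP 9.2 states that treatment-emergent events in the gastrointestinal system organ class (SOC) "will also be summarized by frequency of episodes (1-3 occurrences vs 4 or more) by PT". It then adds: "Similarly, treatment-emergent treatment-related gastro-intestinal adverse events will be summarized". Neither sentence gives a period, a denominator or a rule for counting an occurrence. All AE summaries are to be shown by subpopulation and overall.

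Four other places bear on this:

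- **Length of exposure.** SAP 9.1 tabulates "The number and percentage of subjects with duration of exposure in each category", in six bands from 12 months or less to more than 60 months. The protocol synopsis (Duration of the Study) says: "Approximate treatment time in the Study is up to 96 months".
- **Staggered entry.** The synopsis (Planned Sample Size) says: "Additional patients may be enrolled after all patients from Study RP103-03 have completed participation". Subpopulation A (RP103-03 completers) therefore started first. SAP 4.2.9 describes the patients who had not taken part in RP103-03 as those aged 6 years or less and kidney transplant recipients, which are subpopulations B and C.
- **Exposure adjustment.** Protocol 11.1 planned "summaries of annualized exposure adjusted AE rates as well as summaries of the incidence of subjects with AEs by study year of onset". SAP section 10 states: "Analysis of annualized exposure adjusted AEs will not be performed". Incidence by year of onset remains, with the last category open-ended from Year 3.
- **Counting rule in the other AE tables.** A patient counts once per SOC and once per PT, so those tables do not show how many episodes a patient had.

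**The concern.** Safety and tolerability form the primary objective, and protocol 4.2.2 reports that adverse events under RP103 were mostly nausea, vomiting and other GI effects. This split is the only summary described in the SAP that shows how often GI events recur in a patient. It has two weaknesses.

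First, a fixed count taken over unequal follow-up is not a measure of frequency. Two groups with the same GI rate will show different proportions with 4 or more episodes if one has been followed longer, and the SAP presents the table by subpopulations that entered at different times.

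Second, GI intolerance often appears under several terms. If the count is made within each PT, a patient with many episodes spread over nausea, vomiting and abdominal pain can be placed in the lower category for every one of them.

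The risk is that a reader of the study report takes this table as a picture of long-term GI tolerability, or compares subpopulations on it, when it can support neither use.

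**Working it through.** The plan gives no rate or target for this table, so there is no stated figure to reproduce. From the documents come the cut of 4, the exposure bands, the 96-month maximum and the RP103-03 clustering. Long-term GI rates, their variation between patients and their split over PTs are not given and are assumed below.

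**1. What the cut means at different exposures.** Annual rate at the cut = 4 / years of exposure.

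| Years | 1 | 2 | 3 | 5 | 8 |
|---|---|---|---|---|---|
| Episodes per year at a count of 4 | 4.0 | 2.0 | 1.33 | 0.8 | 0.5 |

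The meaning of the cut changes 8-fold (4.0 / 0.5) between 1 and 8 years. This step needs no assumption.

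**2. Effect on the proportion with 4 or more.** If all patients share one rate r, P(4 or more) = 1 − F(3; r × years), where F is the Poisson distribution function. If rates vary as a gamma distribution with coefficient of variation CV, the count is negative binomial with mean r × years and shape 1/CV².

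| Assumption | 1 year | 2 years | 5 years | 8 years |
|---|---|---|---|---|
| r = 0.5, shared rate | 0.2% | 1.9% | 24.2% | 56.7% |
| r = 1, shared rate | 1.9% | 14.3% | 73.5% | 95.8% |
| mean r = 1, CV 2 | 9% | 18% | 31% | 38% |
| mean r = 1, CV 3 | 9% | 14% | 21% | 25% |

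Within each row tolerability is the same throughout. Strong variation between patients flattens the gradient but does not remove it: at CV 2 the proportion still rises about fourfold from 1 to 8 years (38 / 9).

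**3. Which CV is plausible.** Protocol 4.2.2 reports that "14 of 24 (60%) drug-related GI AEs occurred in 2 patients only". In simulations of 24 events among 43 patients, the two highest patients together held at least 14 events with probability about 0.0003 at CV 1, 0.01 at CV 1.5, 0.08 at CV 2 and 0.44 at CV 3. This points to a CV of about 2 or more, although the data cover only 3-week crossover periods.

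**4. How much of the split is follow-up.** Take follow-up uniform on 0.5 to 6 years and a mean rate of 1 per year, both assumed. The shares of variance in the 4-or-more flag are:

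| CV | Explained by follow-up | Explained by the patient's own rate |
|---|---|---|
| 0.5 | 22% | 19% |
| 1 | 12% | 41% |
| 2 | 4% | 64% |
| 3 | 2% | 74% |

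At the CVs suggested by step 3, the patient's own rate dominates at the individual level. Step 2 shows that a difference between groups with unequal follow-up remains all the same.

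**5. Counting within PT.** Over k terms, up to 3 × k episodes can occur without any term reaching 4: 9 over 3 terms, 15 over 5. With an assumed 2 episodes per year for 3 years (mean 6) split equally over k terms, P(4 or more in at least one term) = 1 − F(3; 6/k)^k.

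| | All GI episodes together | k = 2 | k = 3 | k = 5 |
|---|---|---|---|---|
| P(4 or more) | 84.9% | 58.1% | 37.0% | 15.8% |

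**The case against.** The strongest reply is that this is one additional descriptive table. No endpoint, test or decision depends on it, and the same data are visible elsewhere. By-subject listings hold every AE. Incidence by year of onset, severity, relationship and discontinuation are tabulated. Exposure is shown by subpopulation, so a reader can see unequal follow-up. Use of gastric-acid-reducing medication, with number of occurrences, is also summarized. All of this is correct. It limits the importance of the point, but none of these summaries counts GI episodes per patient on a time scale.

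Four stronger readings are tempting, and the documents do not support them.

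- **That the table mainly reflects length of follow-up.** This would hold if patients had similar GI rates. The RP103-03 clustering suggests that they do not, and then the patient's own rate explains more of the split. That evidence comes from 3-week periods and does not settle long-term rates, but nothing in the documents establishes follow-up as the main driver.
- **That subpopulation A will look worse than B and C.** A entered first and so has longer potential follow-up. The documents give neither actual exposure by subpopulation nor underlying rates, and no formal comparison is planned.
- **That heavily affected patients are hidden.** The listings show them. The RP103-03 text gives neither the split of the 14 events between the two patients nor their terms. If the events fell mostly under one PT, the planned table would show the clustering.
- **That no SOC total will appear.** By PT most naturally means within each PT, but the SAP does not define the count. Its list of tables (section 12) is not legible in the public copy, so a total row cannot be excluded. Such a row would still lack a time unit.

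**Conclusion.** The point holds as a limitation of one descriptive summary. As SAP 9.2 is written, the split is confounded with exposure and is not comparable between patients or subpopulations followed for different times. It can also place a patient with many GI episodes under several terms in the lower category throughout. The exposure-adjusted rates that would have supplied a time scale were planned in the protocol and dropped in the SAP.

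The 8-fold change in the meaning of the cut between 1 and 8 years is plain arithmetic. The proportions are illustrations at assumed rates: 2% to 96% with one shared rate of 1 per year, and about 9% to 38% with the same mean and CV 2. The loss from counting within PT (84.9% to 37.0% in the three-term example) assumes equally frequent terms and a count made strictly within PT.

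The change is worth making because this is the only described summary of GI episode frequency per patient in a study whose primary objective includes tolerability. It does not threaten the study's conclusions on its own.

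**What to change.** In SAP 9.2:

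1. Count all treatment-emergent episodes in the gastrointestinal disorders SOC per patient, and keep the PT table as a breakdown. State how an occurrence is counted.
2. Show the number and percentage of patients with 0, 1-3 and 4 or more episodes in the first 12 months on RP103.
3. Give GI episodes per patient-year of RP103 exposure, by subpopulation and overall, with exposure as defined in SAP 9.1. That definition subtracts days on Cystagon, so the text should also say how episodes starting on those days are treated.
4. Do the same for treatment-related GI events.

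The cost is SAP wording and reprogramming of two tables. The AE onset dates are already needed for the year-of-onset summaries, and the exposure variable already exists. Patients with under 12 months' exposure must be footnoted or shown separately. Displays for later years are better left out or kept secondary: with at most 60 patients the cells would be sparse, and they would include only patients still on treatment, who are likely to be those who tolerate the drug. A rate per patient-year can be dominated by a few patients, so it should stand beside the categorical display and not replace it.

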### **9.3. Laboratory Data**

Clinical laboratory values will be expressed using SI units.

Hematology, chemistry, and urinalysis results will be summarized for each lab parameter at baseline, each collected postbaseline visit, and change from baseline using descriptive statistics (number of subjects, mean, median, SD, and minimum and maximum values). In the event of repeat values, the last non-missing value per visit, per timepoint will be used. If there are multiple records for the same visit and timepoint, the average of the values will be used.

Analysis of individual subject changes will be summarized by shift tables, which will be generated for hematology and serum chemistry parameters. These tables will show the number of subjects who had values that shifted from low, normal, or high at baseline to low, normal, or

---

high at each collected visit.

All laboratory data will be provided in data listings. Values outside of the reference range will be flagged.

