### 4.2. Background

Cystinosis is an autosomal recessive inborn error of metabolism in which the transport of cystine out of lysosomes is reduced or absent. Cystinosis is a rare disease characterized by the accumulation of cystine and formation of crystals damaging various organs, especially the kidney, leading to renal tubular Fanconi Syndrome and progressive glomerular failure, with end stage renal failure by the end of the first decade of life. In four studies of cystinosis patients before cysteamine was available, renal death (need for transplant or dialysis) occurred at median age of less than 10 years (Cystagon® Package Insert, 2007). Patients with cystinosis also experience growth failure, rickets, and photophobia due to cystine deposits in the cornea. With time, most organs are damaged, including the retina, muscles and central nervous system (Cystagon® Package Insert, 2007). Cysteamine is an aminothiol that reacts within lysosomes resulting in a thiol-disulfide interchange reaction that converts cystine into cysteine and cysteine-cysteamine mixed disulfide, both of which can exit the lysosome in patients with cystinosis (Cystagon® Package Insert, 2007).

Cystinosis currently affects approximately 500 people in the United States and 800 in Europe. Children with the disorder, if untreated, suffer progressive kidney failure, damage to multiple organs and a failure to grow to normal height. Most children who suffer this condition undergo kidney transplantation, typically in the first decade of life (Gahl, Balog et al. 2007). Cystagon® capsules contain cysteamine bitartrate, a cystine-depleting agent, which needs to be administered every 6 hours (Q6H) around the clock. This regimen has been associated with poor adherence. There is evidence that such failure to adhere to the strict Q6H dosing regimen results in more rapid deterioration of kidney function (Kleta, Bernardini et al. 2004) and the need for earlier hemodialysis and kidney transplantation in poorer adherent patients.

Cysteamine is moderately bound to human plasma proteins, predominantly to albumin, with mean protein binding of about 52%. Plasma protein binding is independent of concentration over the concentration range achieved clinically with the recommended doses (Cystagon® Package Insert, 2007).

The pharmacokinetics and pharmacodynamics of Cystagon® were studied in eleven pediatric patients with nephropathic cystinosis who received 225 to 550 mg of

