#### 4.2.2. Study RP103-03

This open-label, randomized, controlled crossover trial was powered to show that a new delayed-release formulation of cysteamine bitartrate, RP103, was non-inferior to the currently approved product, an immediate release cysteamine bitartrate, Cystagon®, in maintaining a surrogate marker, white blood cell (WBC) cystine as low as baseline under stable Cystagon® treatment or up to 0.3 nmol  $\frac{1}{2}$  cystine/mg protein greater (non-inferiority margin). Subjects were stratified by their WBC cystine baseline value (0 to 1 nmol  $\frac{1}{2}$  cystine/mg protein or 1 to 2 nmol  $\frac{1}{2}$  cystine/mg protein) before being randomized either to Cystagon® or RP103, treated for 3 weeks, and then crossed over to the other cysteamine therapy. RP103 was started at 70% of the daily dose of the Cystagon® daily dose, but could be adjusted once based on WBC cystine levels measured at the beginning of the RP103 arm of the crossover. Patients were asked to stop using proton pump inhibitors (PPIs) and any anti-acid medication while on RP103.

Forty-three (40 children and 3 adults) patients with cystinosis and with native kidney function based on an estimated GFR (corrected for body surface area)  $> 30$  mL/minute/1.73 m^2 were randomized. Thirty-eight patients were included in the per-protocol primary efficacy analysis. Using a mixed effects statistical analysis model, the least-square-mean peak value of WBC cystine level after 12 hours under RP103 was  $0.62 \pm 0.05$  nmol  $\frac{1}{2}$  cystine/mg protein and after 6 hours under Cystagon® was  $0.54 \pm 0.05$  nmol  $\frac{1}{2}$  cystine/mg protein, with the difference between treatments determined as  $0.08 \pm 0.04$  nmol  $\frac{1}{2}$  cystine/mg protein (95.8 % confidence interval 0 to 0.16). The average, steady-state, total daily dose of RP103 for patients completing the clinical trial was 82% of their incoming, steady-state total daily dose of Cystagon®.

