Pharmacokinetic (cysteamine) and pharmacodynamic (WBC cystine) profiles after RP103 over 12 hours were comparable to PK and PD profiles after Cystagon® over 6 hours. There were no unexpected side effects compared to using Cystagon® and all patients who regularly used PPIs or antacid medication while under Cystagon® but one, were able to discontinue regular concomitant PPI or antacid medications while under RP103, which might account for the higher proportion of reported gastro-intestinal (GI) adverse events under RP103 vs. Cystagon®.

Patient Characteristics

Forty-three patients were randomized. Thirty-eight patients were included in the primary efficacy analysis, as defined beforehand in the statistical analysis plan.

The Intent-To-Treat (ITT) population has 5 more patients than the Per-Protocol (PP) population: 1) two siblings withdrew from the study because one of them had pre-study planned orthopedic surgery, unrelated to disease or treatment, and the family decided to withdraw both children related to travel difficulties; 2) three subjects had a 3-day average WBC cystine level  $> 2$  nmol  $\frac{1}{2}$  cystine/mg protein during one of the periods under Cystagon® and could not therefore be considered as well controlled under Cystagon®, as pre-specified the Statistical Analysis Plan. Patients were mostly children, male or female, with an average age of almost 12 years old.

The first initiated US center enrolled slightly more patients than the other sites that were initiated afterwards. Seven patients were screened twice because the first time their WBC cystine level  $> 1$  nmol  $\frac{1}{2}$  cystine/mg protein and had therefore to be terminated early. They came back after an amendment to the protocol modified this limit and allowed six of these patients with  $< 2$  nmol  $\frac{1}{2}$  cystine/mg protein to be enrolled. Baseline characteristics are summarized in **Table 2**.

	ITT: Intent-To-Treat	PP: Per Protocol
N	43	38
Age (year)	11.7 ± 4.2	11.9 ± 4.4
Children (2 < age <= 12)	27	25
Adolescents (12 < age <= 21)	15	15
Adults (>21)	1	1
Male (n / %)	24 / 56 %	22 / 58 %
Height (cm)	139.5 ± 18.9	139.1 ± 19.1
Weight (kg)	36.0 ± 14.2	34.5 ± 12.1
Body Mass Index (kg/m^2)	17.8 ± 2.8	17.2 ± 2.1
Body Surface Area (m^2)	1.17 ± 0.30	1.14 ± 0.28
Daily Cystagon® Dose (mg)	1,849 ± 536	1,801 ± 511

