### **6.3. Duration**

Patients will be followed until Study termination; which can occur by patient, physician or Sponsor request, or until the RP103 drug is available through the appropriate marketing approval, or until the Sponsor terminates development of RP103 for this indication for any reason. Approximate treatment time in the Study is 96 months. However, a subject may withdraw consent or be withdrawn from the study prior to completion.

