### **3. SUBJECT POPULATIONS**

#### **3.1. Population Definitions**

Two populations for this study are planned for analysis as described below.

**Safety Population:** The Safety Population consists of all subjects who received at least one dose of study drug (RP103).

**PK/PD Population:** All subjects who have at least one PK/PD measurement are included in the PK/PD population.

Each one of these 2 populations is then partitioned in 3 subpopulations:

A: Subjects who completed Study RP103-03

B: Subjects  $\leq$  6 years old

C: Renal Transplant subjects

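### SAP 9.3 does not separate laboratory values taken after an on-study kidney transplant, so a failed native kidney can be tabulated as stable or improved creatinine

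*SAP*

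**What the plan says.** SAP 9.3 covers every laboratory value on study: "Hematology, chemistry, and urinalysis results will be summarized for each lab parameter at baseline, each collected postbaseline visit, and change from baseline". For hematology and serum chemistry it adds shift tables: "These tables will show the number of subjects who had values that shifted from low, normal, or high at baseline", set against the category at each collected visit. Protocol Table 9 places creatinine and blood urea nitrogen in the chemistry panel. SAP 4.2.1 defines baseline as the last non-missing measurement before the first dose. SAP 4.2.7 plans no exclusions for withdrawal or dropout, and SAP 4.2.8 plans no imputation.

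SAP 3.1 defines subpopulation A by completion of RP103-03 alone, and a third group as "C: Renal Transplant subjects", without saying when the transplant must have occurred. SAP 4.2.9 describes kidney transplant recipients as subjects who had not taken part in RP103-03, which points to status at entry.

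Protocol 4.2.2 says that RP103-03 randomized "patients with cystinosis and with native kidney function based on an estimated GFR" above 30 mL/minute/1.73 m². Protocol 6.3 gives the follow-up: "Approximate treatment time in the Study is 96 months"; the synopsis says up to 96 months.

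**The concern.** Long-term safety is the primary objective, and the kidney is the organ that Protocol 4.2 describes as failing progressively in this disease. If a completer is transplanted during follow-up and keeps attending visits, creatinine and urea then come from the graft. The table still reads them as change from the native-kidney baseline. A high creatinine at baseline can become a high-to-normal shift, and the group mean moves in the favourable direction because a kidney failed.

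The visible text does not take such a subject out of the table. Protocol 7.3 makes removal discretionary and names neither transplant nor dialysis. The individual dosing rule in Protocol 10.1.1 is limited to events not likely related to the underlying disease. Transplant recipients are themselves a studied group, so a transplant is no bar to participation.

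**Working it through.** The documents give no figure to reproduce, and no creatinine values or transplant rate. The arithmetic below shows direction and plausible size on assumed values only.

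**Number of subjects.** RP103-03 randomized 43, and Protocol 4.2.2 records that "two siblings withdrew from the study because one of them had pre-study planned orthopedic surgery" and that both children left. Subpopulation A is therefore at most 43 − 2 = 41. The number who enrolled in RP103-04 is not given.

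**Formula.** With k transplanted subjects among N at a visit, and all others drifting by +10 micromol/L (assumed):

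mean change = [k × (value used − baseline) + (N − k) × 10] / N

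**Main illustration.** N = 41, baseline 150, end-stage value 500, post-transplant value 100 micromol/L, all assumed. For k = 4:
- Post-transplant values kept, as SAP 9.3 does: [4 × (100 − 150) + 37 × 10] / 41 = 170 / 41 = +4.1.
- Last pre-transplant value used instead: [4 × (500 − 150) + 37 × 10] / 41 = 1770 / 41 = +43.2.
- Transplanted subjects simply cut off at the event: the other 37 give +10, the same as with no failures at all.

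| k | values kept (SAP 9.3) | cut off at event | last pre-event value |
|---|---|---|---|
| 1 | +8.5 | +10 | +18.3 |
| 2 | +7.1 | +10 | +26.6 |
| 4 | +4.1 | +10 | +43.2 |
| 6 | +1.2 | +10 | +59.8 |

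**Other assumed values, k = 4.** Baseline 110 and post-transplant 90 give +7.1. Baseline and post-transplant both 130 give +9.0. Each is below +10, so the direction holds, but the size depends on the assumed values.

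**Subjects starting near the entry limit.** The documents give no eGFR formula. Under an assumed bedside Schwartz formula and the RP103-03 mean height of 139.5 cm (SD 18.9), an eGFR of 30 corresponds to a creatinine of about 170 micromol/L. In that formula creatinine is proportional to height, so one SD either way gives 170 × 120.6 / 139.5 = 147 to 170 × 158.4 / 139.5 = 193. Four of 40 subjects falling from 170 to 100 move the mean by 4 × (−70) / 40 = −7, with a range of −4.7 to −9.3.

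**Late visits.** With a fall of 50 per transplanted subject and +10 in the others, the mean change turns negative when 50k exceeds 10(N − k), that is, when k exceeds N / 6. This takes 7 of 41, 4 of 20 or 2 of 10 subjects.

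**How many events.** At assumed annual rates of 1% to 5%, expected starts of renal replacement among 41 completers are 41 × (1 − e^(−rate × years)). That is 1.2 to 5.7 over 3 years and 3.2 to 13.5 over 8 years.

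**Dialysis.** With an assumed creatinine of 500 on dialysis and a baseline of 130, k = 1 gives (370 + 400) / 41 = +18.8 and k = 6 gives (2220 + 350) / 41 = +62.7. On creatinine, dialysis would still look like worsening.

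**The case against.** **The failure is reported elsewhere.** Inpatient hospitalization makes an event serious (Protocol 10.1), so a transplant would normally appear in the serious adverse event tables by preferred term, subpopulation and study year. All laboratory values are listed, and shift tables at earlier visits would still show deterioration before the transplant. This stands: a reader might infer that renal failure disappears from the report, and the documents do not support that. The distortion is confined to the laboratory summary and shift tables. The adverse event tables do not correct those, however. SAP 9.2 pools all onset from Year 3 onwards, SAP 10 drops the exposure-adjusted analysis, and no visible display links renal replacement to the laboratory tables.

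**Redaction.** The abbreviation eGFR is listed in the SAP but used nowhere else in its visible text, and text after SAP 8.2 is blacked out. A renal analysis with its own rule may be there. This stands as a limit, although SAP 9.3 shows no redaction and refers to no such rule.

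**The event rate is unknown.** Protocol 4.2 says "Most children who suffer this condition undergo kidney transplantation, typically in the first decade of life", but this follows a sentence about untreated children. RP103-03 subjects were treated and averaged 11.7 years with native kidneys. A reader might infer a high on-study transplant rate; the documents give none. Nor do they establish that transplanted subjects stay and are sampled.

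**A cut-off alone does not help.** It gives +10, the same as with no failures, because the failing subjects leave the late tables. This is correct and shapes the fix.

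**Conclusion.** The point holds as a gap in the plan. As written, SAP 9.3 would count a transplanted subject's graft values as change from a native-kidney baseline, within the subpopulation in which the subject entered. On the assumed values, four transplants among 41 completers bring the reported mean change to +4.1 instead of +10. With four of 40 starting near 170 the pull is about −7 micromol/L. These figures rest on assumed creatinine levels, an assumed count, and subjects remaining on study after transplant. If SAP 3.1 were read as moving such a subject into the transplant group, the values would leave subpopulation A but remain in the overall table.

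Three stronger readings are tempting and not supported:
- **A much larger pull.** Starting from an end-stage creatinine such as 350 would give 4 × (100 − 350) / 40 = −25. SAP 4.2.1 measures change from the pre-dose baseline, and these subjects entered RP103-03 with eGFR above 30.
- **Dialysis looks like improvement.** Creatinine would usually stay high. The narrower point is that the values no longer measure native function.
- **Transplant recipients are analysed separately because their laboratory values differ.** The documents give no reason for the grouping, and the point does not need one.

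**What to change.** In the SAP:
- In 3.1, state that subpopulation membership is fixed at study entry.
- In 9.3, for subjects entering with native kidneys, show the renal chemistry and urinalysis summaries, and the chemistry shift tables, separately before and after the first transplant or dialysis start. Keep all values in the listings.
- Beside each renal table, report the cumulative number and the time of first transplant or dialysis, by subpopulation.
- Add a sensitivity summary that carries the last pre-event value forward, because truncation alone removes the failing subjects from late visits. Name it as an exception to the no-imputation rule in 4.2.8, and present it as a sensitivity analysis.
- If redacted text already defines a renal replacement rule, refer to it from 9.3.

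The cost is SAP wording, one derived date per affected subject from adverse event and medical history records, and a few more table rows. No new data collection and no change in patient care are involved. The downside is that late native-kidney summaries rest on fewer, selectively retained subjects, so the event count and the sensitivity summary must be shown with them.
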